### **Subject selection criteria**

Written informed consent will be obtained from all subjects before enrollment. Once participants have been appropriately consented, the minimal amount of clinical data required will be abstracted from their electronic medical record. Other extracted information will include their past medical history, such as comorbidities, current medications, and any symptoms of IC they experience. Furthermore, physical exam findings, laboratory results, intra-operative findings, and pathology reports will be reviewed. Patients will complete questionnaires that have been well-established to assist in IC diagnosis and assessment of disease severity and response to treatment, and are part of routine clinical diagnosis and treatment. These include the O'Leary-Sant Interstitial and the Pelvic Pain and Urgency/Frequency Patient Symptom Scale (PUF). Each of these questionnaires are well established in the literature to help the urologist identify and treat patients with IC. Their scores on these questionnaires must >10 for either the ICSS or ICPI, and >10 on the PUF. Both the O'Leary/Sant questionnaire and PUF questionnaire ask about the voiding patterns and pain levels of IC patients.

### **Inclusion Criteria**

#### **Subjects should only be included if they meet the following conditions:**

1. Adult females between the ages of 18 and 80 inclusive
2. Patients being treated for IC who are refractory to conservative management and oral therapy.
3. willing and able to initiate catheterization post-treatment

These patients will all have undergone evaluation by [name], an expert in the management of pelvic pain syndromes who sees >300 new patients each year. Subjects will be drawn from the patient population undergoing chronic management for their IC. The clinical diagnosis of IC will be based on the recently published AUA Guidelines definition: "An unpleasant sensation (pain, pressure, or discomfort) perceived to be related to the urinary bladder, associated with lower urinary tract symptoms for more than six weeks duration, in the absence of infection or other identifiable causes."

### **Exclusion Criteria**

#### **Subjects should be excluded if any of the following applies:**

1. Any history of bladder cancer, uterine cancer, ovarian cancer, vaginal cancer, urethral diverticulum, spinal cord injury, stroke, Parkinson's disease, multiple sclerosis, spina bifida, cyclophosphamide treatment, radiation treatment to the pelvis, bladder tuberculosis, genital herpes.
2. Currently on or requiring anti-platelet/anti-coagulant concomitant therapy or having been on anti-platelet/ anti-coagulant therapy within the past 3 months

3. Pregnancy. Pregnancy is an absolute contraindication to undergoing these procedures. Thus, as part of their normal pre-operative work up, which is standard of care, pregnancy tests are administered if they are women of child-bearing age, are sexually active, and are within 10 days of the normal menstrual period. If positive, they will be excluded as they will not undergo the procedure.
4. An active urinary tract infection as shown during clean-catch urinalysis at screening visit. Subject may be re-screened if UTI is successfully treated and urinalysis is negative at rescreening.
5. A history of hypersensitivity or allergy to any botulinum toxin preparation
6. A post-void residual (PVR) urine volume >200mL at baseline
7. Treatment with botulinum toxin during the 12 week period prior to the trial
8. Current treatment with aminoglycosides or other drugs that interfere with neuromuscular transmission or with muscle relaxants.

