After the procedure subjects will be scheduled for clinical follow-up at 2 weeks for a measurement of post void residual and adverse event collection. At the day 30 and 90 day follow-up visits patients will again undergo evaluation including collection of adverse events, concomitant medications, history taking and physical examination, urinalysis, subjective symptom assessment using self-reporting questionnaires, and objective symptom assessment using uroflowometry as well as the measurement of post void residuals. At day 45 and day 60 we will call to verify if patient has had any adverse events or changes in concomitant medications. We will then analyze the data generated by these follow-up visits to measure the efficacy of Onabotulinumtoxin A injections for interstitial cystitis as well as impact of injection location, if any.

Procedures, Tests and Evaluations	Screening and Baseline Study Day 0 in Clinic	Week 2 Clinic visit	Day 30 Clinic Visit	Day 45 Phone call	Day 60 Phone call	Day 90 Clinic Visit
	Day 0	Day 14 ±3	Day 30 ±3	Day 45 ±3	Day 60 ±3	Day 90 ±3
Informed Consent	X					
Medical History/Demographics	X					
Medical History verification		X	X			X
Concomitant Medications	X	X	X	X	X	X
Inclusion/Exclusion Verification	X					
Physical Examination (PE)	X		X			X
Uroflowometry	X		X			X
Pregnancy Test	X a					
Antibiotic dose	X					
Post-Treatment Observation and Void	X b					
Urinalysis/Urine Culture	X		X			X
Questionnaires—PUF, O’Leary-Sant	X		X			X
Bladder Post-void Residual	X	X	X			X
IP injections	X					
AEs	X	X	X	X	X	X

- a. For subjects who are of child-bearing potential
- b. Subjects will remain at site on Day 0 after treatment for at least 30 minutes for observation. Subjects must also demonstrate their ability to void before leaving.

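### Exclusion 3 states a narrower pregnancy-test rule than footnote a of the visit schedule, and the protocol does not say which one governs

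*Combined protocol and SAP*

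**What the plan says.** Item 3 of the Exclusion Criteria names pregnancy as an exclusion and adds that "Pregnancy is an absolute contraindication to undergoing these procedures". It then explains how this is put into effect: "Thus, as part of their normal pre-operative work up, which is standard of care, pregnancy tests are administered" if the woman is of child-bearing age and two further conditions hold, namely that such women "are sexually active, and are within 10 days of the normal menstrual period". The item ends with the consequence: "If positive, they will be excluded as they will not undergo the procedure". The list is headed "Subjects should be excluded if any of the following applies", so pregnancy itself excludes without condition.

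The schedule of procedures under Design has a separate row for the pregnancy test, marked in the column headed "Screening and Baseline Study Day 0 in Clinic". Its only qualifier is footnote a: "For subjects who are of child-bearing potential". The same column holds the row "Inclusion/Exclusion Verification" and the row for the injections.

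Pregnancy testing is mentioned nowhere else in the protocol. No section says whether the schedule or the eligibility text governs where they differ.

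**The concern.** The test is there to find a pregnancy that the woman does not know about. Both extra conditions in item 3 weaken it for that purpose. One rests on what the woman reports about sexual activity. The other rests on a time window that the protocol does not define further: it could run before the period, after it, or on both sides.

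Eligibility, the test and the single injection all fall on Day 0, and the schedule shows no later pregnancy test and no separate pre-injection visit. A test left out on Day 0 would therefore not be caught before treatment. Inclusion criterion 1 admits women from age 18, so the situation can arise. What is at stake is the safety of a participant, and of a fetus, in a case where the protocol itself allows no exception.

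**Working it through.** The plan gives no figure to reproduce. The check is a comparison of two rules.

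**Inputs**

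- Rule A (Exclusion Criteria, item 3): test if the woman is of child-bearing age AND sexually active AND within the 10-day window.
- Rule B (schedule, footnote a): test on Day 0 if the woman is of child-bearing potential.

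**Step 1: hold the population fixed.** For the count, treat child-bearing age and child-bearing potential as the same group. This is a simplification. A surgically sterile woman of child-bearing age could meet Rule A but not Rule B. For women of child-bearing potential, the group that matters here, Rule A is the narrower rule.

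**Step 2: list the case types.** Two yes/no conditions remain, giving 2 × 2 = 4.

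| Sexually active | Within 10-day window | Rule A (item 3) | Rule B (footnote a) | Same? |
|---|---|---|---|---|
| Yes | Yes | Test | Test | Yes |
| Yes | No | No test called for | Test | No |
| No | Yes | No test called for | Test | No |
| No | No | No test called for | Test | No |

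Rule A calls for a test in 1 case type and Rule B in 4, so they differ in 4 − 1 = 3 of 4. These are kinds of situation and carry no weights. They do not say what fraction of women falls in each row.

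**Step 3: illustrate the window alone.** Assume a 28-day cycle, which is not in the documents. A 10-day window on one side of the period leaves (28 − 10)/28 = 18/28, or 64%, of cycle days outside it. A window of 10 days on each side leaves (28 − 20)/28 = 8/28, or 29%. The range shows how much turns on a term the protocol leaves open. It is not an estimate of missed tests.

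**Step 4: look for a rule of precedence.** There is none. Item 3 introduces its testing conditions as following from the contraindication and then states what a positive result means. A reader can reasonably take it as the operative procedure.

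**Step 5: cost of harmonising to Rule B.** Rule B is already scheduled, so the tests added beyond footnote a are 4 − 4 = 0 case types.

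**The case against.** The best defence is that the two texts are compatible. Item 3 can be read as a description of routine pre-operative care, with the schedule adding the study's own test. It says tests are given if the conditions hold. It does not say only if, and it does not forbid wider testing. A site that follows footnote a breaches nothing in item 3. Harm would need three things together: staff pass over an explicit schedule row, the woman falls outside the item 3 conditions, and she is unknowingly pregnant. The documents give no means of saying how likely that is. The count of case types restates the logic of conditions joined by *and*, and says nothing about prevalence.

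Much of this stands. The schedule does carry the safer rule, the consequence is conditional, and the count should not be read as a measure of frequency. What does not stand is the inference that nothing needs changing. The conditions sit inside a numbered exclusion criterion, are presented as the means of enforcing it, and are followed by the action on a positive result. A coordinator working through the criteria on Day 0 meets the narrower rule and could take footnote a as shorthand for it. That an unconditional exclusion also exists helps only when the pregnancy is already known.

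**Conclusion.** The concern holds. The protocol gives two different testing rules for the same safety check and no order of precedence. Applied literally, item 3 would leave some women of child-bearing potential untested before a treatment the protocol says must not be given in pregnancy.

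The point is limited in size. It matters only where staff use item 3 as the testing rule, and how many women that would affect cannot be estimated from the documents. The conclusion rests on the wording alone. It needs no assumption about cycle length or pregnancy rates. There is no consequence for the sample size of 40, the type I error, the power or the comparison of injection sites. It is a small safety harmonisation that should be made.

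**What to change.** In Exclusion Criteria, item 3, replace the sentence that sets the three testing conditions with:

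> Every subject of child-bearing potential must have a negative pregnancy test on Day 0 before injection, regardless of reported sexual activity or cycle day.

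Keep pregnancy as the unconditional exclusion, keep the sentence on a positive result, and leave footnote a as it is. The new sentence also fixes the order of test and injection, which the schedule marks on the same day without saying which comes first. The protocol does not define child-bearing potential, so a short definition in the same amendment would be a sensible addition.

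The cost is one sentence in a protocol amendment, plus the definition if adopted. No tests are added beyond those footnote a already schedules. Compared with a site now working to item 3, some tests would be added, but their number cannot be estimated from the documents. No ceiling per subject can be given either, because exclusion 4 allows re-screening after a treated urinary infection and a test may then be repeated.

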### **Sample Size and Randomization**

Each study arm will consist of 20 subjects for a total study population of 40. This number was chosen using estimates of symptom relief using our current patient population as reference.

Patients will be randomized to either the control or experimental cohort using a computer generated randomization table. Providers will not be aware of the subjects' cohort status until immediately prior to injection.

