## **MATERIALS AND METHODS**

### **Design**

This is a single center, prospective, randomized clinical trial. Subjects will consist of patients referred to the urology clinic at Wake Forest University Baptist Medical Center with interstitial cystitis for whom conservative management/oral medications have failed and Onabotulinumtoxin A is recommended. These patients will all have undergone evaluation by [name]: an expert in the management of pelvic pain syndromes who sees >300 new patients each year.

Upon initial evaluation all subjects will undergo assessment including history taking and physical examination, urinalysis, subjective symptom assessment using self-reporting questionnaires, and objective symptom assessment using uroflowometry as well as the measurement of post void residuals.

After initial assessment subjects will be randomized into either the control or experimental cohorts. Subjects will receive a single dose of PO ciprofloxacin prior to injection unless culture or allergies dictate to use a different antibiotic. Each group will receive a total of 100 units of botox spread out among 10 separate injections. Subjects in the control group will have 10 injections made about the periphery of the trigone.

Subjects in the experimental cohort will receive a one time dose of 100 units of Onabotulinumtoxin A diluted in 10 mL of preservative free normal saline and injected in 1.0 mL boluses in a set pattern across the upper aspect of the trigone of the urinary bladder. Meanwhile, those subjects randomized to the control cohort will also receive a one time dose of Onabotulinumtoxin A using the same dilution and number of boluses, but boluses will be administered at random sites on the posterior bladder wall (excluding the trigone). Post –treatment, subjects will remain at the site for at least 30 minutes for observation and will demonstrate their ability to void before leaving. All procedures will be performed using the facilities of Wake Forest Baptist Medical Center.

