### **Outcome Measure(s)**

The primary outcome will be a measurement of subjective patient pain using the Pelvic Pain and Urinary Urgency Frequency (PUF) questionnaire and the O'Leary-Sant Symptom and Problem Indexes. Patients will be asked to complete this questionnaire prior to treatment administration and at 30 and 90 days post treatment. The PUF and O'Leary Sant are previously validated tools that have been used by numerous researchers to evaluate pelvic pain. Secondary outcomes will be objective data as to patient performance in uroflowmetry as well as measurement of post void residuals. Patients will

again undergo these assessments prior to treatment and at 30 and 90 days post treatment to assess objective treatment effectiveness.

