### **Human Subjects Protection**

**Informed Consent:** An IRB approved written informed consent will be obtained from each subject. [name] or the study coordinator will consent each of the potential subjects. Informed consent will be acquired in the day hospital at Wake Forest University, or in the Wake Forest University Urology Out-patient Clinic.

**Confidentiality and Privacy:** Confidentiality will be protected by collecting only information needed to accomplish age and gender matching (i.e. patient's age and patient gender), minimizing to the fullest extent possible the collection of any information that could directly identify subjects, and maintaining all study information in a secure manner. To help ensure subject privacy and confidentiality, only a unique study identifier will appear on the data collection form. Any collected patient identifying information corresponding to the unique study identifier will be maintained on a separate master log. The master log will be kept secure, with access limited to designated study personnel. Following data collection subject identifying information will be destroyed at the earliest opportunity, consistent with data validation and study design, producing an anonymous analytical data set. Data access will be limited to study staff. Data and records will be kept locked and secured, with any computer data password protected. No reference to any individual participant will appear in reports, presentations, or publications that may arise from the study.

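### The only stated masking rule ends just before injection; nothing in the protocol body keeps the injection site from the patient, who rates the primary outcome, through day 90

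*Combined protocol and SAP*

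**What the plan says.** Under Sample Size and Randomization, after describing a computer-generated allocation table, the protocol gives its single rule on masking: "Providers will not be aware of the subjects' cohort status until immediately prior to injection".

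The Design section describes the study in one phrase, "This is a single center, prospective, randomized clinical trial", with no statement that anyone is blinded and none that the trial is open-label. The visit schedule, the Analytical Plan and the Data and Safety Monitoring section add no rule on who may know the allocation after treatment.

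The outcome comes from the patient. Outcome Measure(s) states: "The primary outcome will be a measurement of subjective patient pain using the Pelvic Pain and Urinary Urgency Frequency (PUF) questionnaire", together with the O'Leary-Sant indexes. The Design section describes the method as "subjective symptom assessment using self-reporting questionnaires". On timing, "Patients will be asked to complete this questionnaire prior to treatment administration and at 30 and 90 days post treatment".

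Two other statements bear on the point. The control arm is treated "using the same dilution and number of boluses" as the experimental arm. The confidentiality paragraph under Human Subjects Protection says that "only a unique study identifier will appear on the data collection form".

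**The concern.** For a self-completed questionnaire the patient is the outcome assessor, so her knowledge of the allocation matters more than anyone else's. The stated rule covers the provider, and only up to the moment when the provider has to know where to inject. Every post-treatment score is collected after that.

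The Background, Objectives and Specific Aims all state the expectation that the trigone is the better site. The injecting provider works with that expectation and knows the site from the injection onward. Nothing in the protocol body stops the site from being passed to the patient, or to staff at the day-14, day-30 and day-90 visits.

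The main comparison is at stake. There is no placebo or untreated arm, and the arms are meant to differ only in where the drug goes. A difference in scores produced by knowing the site would look exactly like an effect of location, and no later analysis could remove it.

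**Working it through.** **Step 1. Sequence of events under the plan.**

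| Time | Event | Stated masking |
|---|---|---|
| Before treatment | Baseline PUF and O'Leary-Sant | Provider does not know the arm |
| Immediately before injection | Provider learns the arm | Rule ends |
| Day 14 | Post-void residual, adverse events | None stated |
| Day 30 | Primary questionnaires, uroflowmetry, post-void residual | None stated |
| Day 90 | Primary questionnaires, uroflowmetry, post-void residual | None stated |

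The stated masking covers none of the post-treatment outcome measurements. It never mentions the patient.

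**Step 2. Reproduce the plan's own figure.** Inputs from the Power Analysis: Cohen's d = 0.95, alpha 0.05, power 0.80 (written there as beta), 19 per arm. Sidedness is not stated. For a two-sample t-test with n per arm, df = 2n − 2 and the noncentrality is δ = d × √(n/2). Power is 1 − F(t*; df, δ) + F(−t*; df, δ), where F is the noncentral t distribution function and t* is the two-sided 5% critical value.

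- n = 18: power 0.791, below 0.80.
- n = 19: δ = 0.95 × √9.5 = 2.93, power 0.813. This is the smallest n that reaches 0.80, so 19 per arm and 38 in total reproduce.
- n = 20 (planned): δ = 0.95 × √10 = 3.00, power 0.833.

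A one-sided test would need only 15 per arm, so the two-sided test is the one that matches. The sample size is not in dispute here; this step only confirms the test used in Step 3.

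**Step 3. What a reporting shift would do.** The documents give no size for such a bias, so a range is assumed. Suppose the sites are truly equal and knowledge of the site moves the between-arm difference by b standard deviations toward the trigone. With n = 20, df = 38 and δ = b × √10:

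| Assumed shift b (SD) | δ | Chance of a significant result | Of which favouring the trigone | b as a share of 0.95 |
|---|---|---|---|---|
| 0 | 0 | 5.0% | 2.5% | 0% |
| 0.1 | 0.32 | 6.1% | 4.9% | 11% |
| 0.2 | 0.63 | 9.5% | 9.0% | 21% |
| 0.3 | 0.95 | 15.2% | 15.0% | 32% |
| 0.4 | 1.26 | 23.4% | 23.4% | 42% |

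These figures describe a single t-test. The plan names more than one questionnaire score at two follow-up times as primary, so they are not the error rate of the plan as a whole.

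**Step 4. Is masking the patient feasible?** According to the Design section, both arms receive the same drug, total units, dilution and number of boluses in one session. Nothing the patient is scheduled to undergo afterwards differs by arm. The protocol body therefore shows no procedural obstacle to withholding the site.

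**The case against.** The strongest reply is that the text is silent, and silence is not an open-label design. A reader might infer that patients are told their site. No section says so, and they may well not be told in practice. The title and consent pages, where a blinding label or a statement to patients could appear, were not available for this review. That part of the reply stands. What can be said is that the protocol body does not state any masking of patients, not that they are unmasked.

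A reader might also infer a demonstrated bias in favour of the trigone. The documents do not show that either. The hypothesis belongs to the investigators, and nothing shows that patients share it or hear it. Both arms receive active drug in the same form, which removes any contrast between treatment and none and probably weakens expectation. The direction is a reasonable inference and the size is unknown. A shift of zero is possible.

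On staff, the patients complete the primary questionnaires themselves, so masking the people who collect them matters less. The protocol describes uroflowmetry and post-void residual as objective. The rule that "only a unique study identifier will appear on the data collection form" helps a little, but it is a confidentiality measure and does not say that allocation is hidden from those who take the measurements.

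Finally, masking might be imperfect. The Background places most of the bladder's pain fibres in the trigone, so injections there could feel different. The documents also do not say who injects and who runs follow-up. Both points limit how complete masking can be. Neither is a reason to leave the matter unstated.

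**Conclusion.** The concern holds in a limited form. The only masking rule in the reviewed text stops immediately before injection, and nothing in the protocol body keeps the site from the patient or from follow-up staff through day 90. With a self-reported primary outcome and location as the only intended difference, knowledge of the site could bias the main comparison.

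The size cannot be taken from the documents. The range in the working, from about 6% to 23% for shifts of 0.1 to 0.4 SD against a nominal 5%, rests on three assumptions: the shift itself, equal true effects at the two sites, and a single two-sided t-test with 20 per arm. It shows that even a modest shift would matter in a trial of this size. It does not show that such a shift will occur.

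This is a cheap improvement to the plan. It is not a finding that the trial is open-label or that its result will be biased.

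**What to change.** Add to Sample Size and Randomization:

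- Subjects are not told their injection site until the day-90 questionnaires are complete, except where disclosure is needed for their care.
- At days 30 and 90, patients complete the PUF and O'Leary-Sant forms themselves before any contact with the injecting provider.
- Where existing staffing allows, those who measure uroflowmetry and post-void residual do not have the allocation.

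Align the consent wording with these rules. If the sponsor concludes that patients cannot be masked, the protocol should describe the trial as open-label after injection, and the conclusion about location should be limited accordingly.

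The cost is a few sentences of protocol and consent text and attention to the order of events at two visits. The sample size, number of visits and treatment do not change. The downsides are that patients wait until day 90 to learn their site and that masking may be imperfect. The rules need to be in place before the first patient is treated, because unmasking cannot be undone in the analysis.
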